Our group identified low circulating levels of betaine in the blood correlate with insulin resistance. Betaine is important in cellular metabolic pathways. Epidemiologic studies link betaine levels to diabetes and cardiovascular disease. Small human studies suggest benefit for non-alcoholic liver disease. We have shown in rodents that betaine levels fall with high fat feeding and there are metabolic improvements with replacement. In this study we will determine if administration of betaine improves metabolic measures, liver fat and/or endothelial function in humans with glucose intolerance who are overweight.

RESEARCH DESIGN AND METHODS

Briefly describe study design and anticipated enrollment, i.e., number of subjects to be enrolled by researchers study-wide and by Partners researchers. Provide a brief summary of the eligibility criteria (for example, age range, gender, medical condition). Include any local site restrictions, for example, "Enrollment at Partners will be limited to adults although the sponsor's protocol is open to both children and adults."

Patient identification: We will identify patients with prediabetes through a screening 75 gram oral glucose tolerance test. Currently, we diagnose 30% prediabetes in screening persons with one or more risk factor for type 2 diabetes [88]. Thus, we anticipate screening 90-100 persons to identify the 30 subjects for this study. Many participants may come from those screened for other ongoing studies at the Joslin Diabetes Center who have expressed interest in participation in additional studies. Persons screened for this study will meet trial inclusion/exclusion criteria including grade 1-3 obesity and one or more diabetes risk factors including: physical inactivity; high risk ethnic population; first degree relative with T2D; women who delivered an infant >9lbs or with gestational diabetes, or with polycystic ovarian syndrome; hypertension (controlled); low HDL or high triglyceride (but <500 mg/dL); age >45 years; or dysglycemia on prior testing.

Inclusion Criteria: 1) Men and women aged 21-70 years old; 2) Dysglycemia/prediabetes is defined as impaired fasting glucose (≥ 100 mg/dl), impaired glucose tolerance (2 hour post 75 g oral glucose load 140-200 mg/dl) and/or HbA1c 5.7-6.5%); 3) Overweight to grade 3 obesity (BMI ≥ 25 to 45 kg/m²).

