Exclusion Criteria: 1) cystathionine beta-synthase (CBS deficiency) (based on medical history and reported family history); 2) Presence of liver disease other than NAFLD; 3) Use of medications causing steatosis 4) Known alcohol consumption ≥ 2 drink per day; 5) Use of medications known to cause insulin resistance; 6) Use of weight loss drugs (or program) within 3 months of screening; 7) Treatment with any experimental drug within the past 6 months; 8) Subjects must be willing to abstain from use of phosphodiesterase type 5 (PDE-5) inhibitors; 9) Pregnancy or lactation, and women of child bearing potential must use adequate contraception; 10) Surgery within 30 days of screening; 11) Heart disease defined as New York Heart Association Class III or IV cardiac status or hospitalization for congestive heart failure, unstable angina, myocardial infarction, cerebrovascular accident, transient ischemic attack or any revascularization within 6 months; 12) Uncontrolled hypertension; 13) eGFR <60; 14) History of acquired immune deficiency syndrome; 15) History of malignancy within 5 years; 16) Hemoglobin <12 g/dL (males), <10 g/dL (females); 17) Triglycerides (TG) >500 mg/dL; 18) Poor mental function or any other reason to expect patient difficulty in complying with study requirements; 19) Metal clips or implants that preclude magnetic resonance imaging.

Briefly describe study procedures. Include any local site restrictions, for example, "Subjects enrolled at Partners will not participate in the pharmacokinetic portion of the study." Describe study endpoints.

We propose a randomized (1:1) double-masked proof-of concept study of betaine administration over 3 months to 30 patients with prediabetes (defined below) and Overweight to grade 3 obesity (BMI ≥ 25 to 45 kg/m²). Betaine will be dosed at 333/0 mg/ml oral suspension, 2 teaspoons (3300 mg; 10 ml) twice daily for 10 days, then 1 tablespoon (4950 mg; 15 ml per dose, 10 g/d total) twice daily for the remainder of the 3 months, the dose used to treat patients with homocysteinuria and tolerated with evidence of benefit in pilot studies in humans with NASH. Participants will have oral glucose tolerance test, euglycemic hyperinsulinemic clamp, MRI of

the liver, and brachial artery flow mediated dilation studies performed at baseline and after 12 weeks of randomized assignment to betaine or placebo.

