Provide a brief description of any foreseeable risks and discomforts to subjects. Include those related to drugs/devices/procedures being studied and/or administered/performed solely for research purposes. In addition, include psychosocial risks, and risks related to privacy and confidentiality. When applicable, describe risks to a developing fetus or nursing infant.

Risks of Taking Betaine

Betaine occurs naturally in the body. It is a metabolite of choline and is present in small amounts in foods such as beets, spinach, cereals, and seafood. However, taking betaine may cause one or more of the side effects listed below.

Common side effects:

- Nausea (2 out of 100 people reported this side effect)
- Gastrointestinal complaints (2 out of 100 people reported this side effect)

Uncommon side effects:

- A few cases of cerebral edema (brain swelling) have been reported in patients with a rare inherited disorder called cystathionine beta synthase (CBS) deficiency.

There may be other risks of betaine that are currently unknown.

As with any drug, an allergic reaction can occur. Allergic reactions can be mild or more serious, and can even result in death. Common symptoms of an allergic reaction are rash, itching, skin problems, swelling of the face and throat, or trouble breathing.

Betaine is pregnancy class C.

Of note that Cystadene 20g/d (twice the amount proposed in this study) is the upper end of the recommended daily dose range for patients with hyperhomocysteinemia: from Cystadane Product Information (package insert).

Betaine doses of 20 g/d for 12 months have been studied in about 30 patients with liver disease, with this number receiving the active betaine. Safety assessment and findings of these published studies are summarized below.

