In the first study, Abdelmalek et al (Am J Gastroenterol. 2001 Sep;96(9):2711-70) surveyed safety with patients contacted by phone by the study coordinator at wk 1, 2, and 4 of treatment, and then monthly for the duration of treatment. At every contact point adverse events, concurrent illnesses, concomitant medications, and compliance with the study medication were assessed. Monitoring laboratory tests including liver biochemistries (ALT, AST, alkaline phosphatase, serum bilirubin, albumin, and prothrombin time), hematology panel, serum creatinine, and glucose were performed at 1, 3, 6, 9, and 12 months during the study. A complete medical history and physical examination were repeated at the end of treatment in each patient. Seven of 10 patients completed 1 yr of treatment with betaine. Two patients moved and were lost to follow-up at 3 and 9 months; and one patient was on treatment for only 6 months as a result of inability to obtain study medication because of a transient shortage in supply by the manufacturer.

Four of 10 patients experienced adverse events during treatment with betaine including nausea, abdominal cramps, loose stools, and body odor. None of these adverse events were dose limiting, and all four patients completed 1 yr of treatment. There were no adverse events noted in hematology or blood chemistry results.

Please note that body odor is not in other reports or the package insert and has not been added to the consent document.

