In the second study, Abdelmalek et al (Hepatology. 2009 Dec;50(6):1818-26) followed safety with patients evaluated at the study center every 3 months and phone communication was made with each study participant on a monthly basis to assess compliance with study medication and development of any adverse events. Of those who completed 12 months of therapy (betaine 17, placebo 18), no changes in weight, BMI, or serum aminotransferases or lipid or laboratory safety monitoring parameters were noted. There was no clinically apparent hepatotoxicity (defined as ALT or AST 3x baseline value) rise in total bilirubin value of 2x normal, or severe adverse events reported in either treatment group. The overall incidence of gastrointestinal adverse events (i.e., nausea, vomiting, abdominal bloating, and/or diarrhea) in those treated with betaine was 33% versus 9%, in those treated with placebo, ($P < 0.05$). A comparable number of patients in each treatment arm were either noncompliant with study drug and/or voluntarily withdrew their participation. Eighteen subjects (nine in each group) voluntarily withdrew consent for adverse effects, noncompliance, and the "inconvenience" of taking study drug, or inability to continue study participation.

The studies in healthy persons at ≥ 6 g/d note similar side gastrointestinal side effects.

Risks of Phlebotomy and intravenous catheters:

Participants may have a bruise (a black and blue mark) or pain where we take the blood samples. There is also a small risk of infection, lightheadedness, and/or fainting.

The total amount of blood drawn during the entire study is approximately 650 ml. This is about 1 ½ pints of blood. Adults can safely donate 1 pint (2 cups) of blood every two months. In this study blood draws will be distributed over visits spanning three months, with most blood drawn at visits 3-4 and 7-8. Participants should delay enrollment into the study if they have given blood (ie at a hospital or the Red Cross) within 2 months, and should not donate blood during the study or for two months after taking part in this study to minimize risk of anemia (low blood counts).

Risks of Oral Glucose Tolerance Test

Nausea or incidental findings

Risks of Use of Insulin

Hypoglycemia

Risks of Use of Glucose

Hyperglycemia

Risks of Use of Nitroglycerin

Headache, dizziness, hypotension, bradycardia

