## **Statistical Plan**

**Sample Size and Data Analysis:** The study will use a single site randomized, double-mask design. Our primary analysis to examine the effect of betaine supplementation will be by change from baseline to 3-month values compared to placebo in completer analysis for all endpoints of Aims 1-3. Safety will be assessed by intention to treat. Prior to data analysis, the data will be examined for outliers. Continuous measures whose distributions are not symmetric will be transformed. In secondary analysis for all outcomes we will determine if baseline betaine determines response to supplementation.

*Insulin Sensitivity*-Basis for power calculations: In an overweight prediabetes population of 14 persons similar to that proposed in this grant and using a similar clamp protocol, we demonstrated insulin sensitivity of  $5.9 \pm 2.1$  mg/kg/min, a value significantly lower than  $8.3 \pm 1.8$  in our normoglycemic control group of 27 patients ( $P=0.0005$ ). This demonstrates likelihood that the cohort proposed will be insulin resistant. We also recently assessed insulin sensitivity by clamp before and after *placebo* in a cohort of 29 persons with impaired glucose tolerance in another 3-month randomized study. Baseline values were  $4.0 \pm 1.5$  mg/kg/min and 3 months later  $4.1 \pm 1.7$ ,  $P=0.3$ . The placebo change over time was  $0.16 \pm 0.81$ , or variance  $<4\%$ . This demonstrates the high reproducibility of clamp measures. A total of 30 patients entering this two-treatment parallel-design study, provides 80% probability of detecting a treatment difference at a paired two-sided comparison with type 1 error 0.05 significance, if the standard deviation is 0.81 and the true difference between treatments is 0.85 mg/kg/min (a between-group difference of 20% change from baseline). Given the short duration of the study, we anticipate  $\geq 80\%$  retention rate, but even 24 completers would detect difference between treatment groups of 0.96 mg/kg/min (25% change from baseline between groups).

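### Does the gap between this trial's 10 g/d and the 20 g/d of the described liver-disease studies leave a null liver-fat result uninterpretable?

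*Protocol*

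**What the plan says.** Protocol, Research Design and Methods (study procedures): a 10-day run-in with two daily doses of 3300 mg each. The maintenance schedule is worded "then 1 tablespoon (4950 mg; 15 ml per dose, 10 g/d total) twice daily for the remainder of the 3 months". The reason given is that this is "the dose used to treat patients with homocysteinuria and tolerated with evidence of benefit in pilot studies in humans with NASH". The pilot studies are not identified.

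Protocol, Background and Significance: "Small human studies suggest benefit for non-alcoholic liver disease", with no dose or duration.

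Protocol, Foreseeable Risks and Discomforts (Risks of Taking Betaine): a package-insert remark about "Cystadene 20g/d (twice the amount proposed in this study", then "Betaine doses of 20 g/d for 12 months have been studied in about 30 patients with liver disease", then safety summaries of two published studies. Of the first it says "Seven of 10 patients completed 1 yr of treatment with betaine". Of 12-month completers in the second, which was placebo-controlled, it says "no changes in weight, BMI, or serum aminotransferases or lipid or laboratory safety monitoring parameters were noted".

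SAP, Statistical Plan: "In secondary analysis for all outcomes we will determine if baseline betaine determines response to supplementation". The endothelial-function paragraph also refers to betaine at baseline only. The liver-fat paragraph gives 80% power for a 3.3-point difference in change, with SD 3.1 and 30 patients in total. The closing paragraph on secondary outcomes accepts that only fairly large effects are detectable.

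**The concern.** Read together, the two Protocol sections seem to disagree about where the evidence was obtained. The procedures section attaches NASH benefit to the trial's regimen. The risk section places the only liver-disease studies it describes at about twice that daily dose and for 12 months instead of 3. Neither summary reports a liver benefit, and the one comparative liver finding is unchanged aminotransferases.

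The second strand is exposure. Compliance checks are mentioned for the two cited studies but not for this trial, and betaine appears in the analysis only as a baseline modifier of response.

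What would be at stake is the reading of Aim 2. If liver fat does not fall, a reader could say that betaine does not work, that this regimen delivers too little, or that participants did not take it. The Expected Benefits section hopes the trial will prepare the way for later trials, so the choice among those readings would matter.

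**Working it through.** **1. The dose ratio, from the documents' own figures.** Run-in: 2 × 3300 mg = 6.6 g/d. Maintenance: 2 × 4950 mg = 9.9 g/d, which the Protocol rounds to 10. Then 20 / 9.9 = 2.02, so the Protocol's own statement that 20 g/d is double the proposed amount reproduces. The inverse is 9.9 / 20 = 49.5%. The gap is real and the Protocol discloses it.

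**2. Cumulative dose.** Over 12 weeks: 10 × 6.6 + 74 × 9.9 = 798.6 g. Against 20 × 365 = 7300 g this is 10.9%. Taking 3 months as 90 days gives 10 × 6.6 + 80 × 9.9 = 858 g, or 11.8%. Most of this contrast is duration: 84 / 365 = 23.0%, and 0.495 × 0.230 = 11.4% before allowing for the run-in. Nothing in the documents says that total grams drive the effect, so the ratio carries little weight.

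**3. Does dose enter the liver-fat sample size?** Inputs from the SAP: SD of change 3.1, two-sided 0.05, 30 patients; 1:1 allocation from the Protocol, so 15 per arm. Two-sample t-test with noncentrality δ / (σ√(2/n)):

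| Per arm | Noncentrality at δ = 3.3 | Power | Difference detectable at 80% |
|---|---|---|---|
| 15 | 3.3 / (3.1 × √(2/15)) = 2.92 | 80% | 3.29 |
| 12 (80% retention) | 3.3 / (3.1 × √(2/12)) = 2.61 | 70% | 3.71 |

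The first row reproduces the SAP's 3.3. The figure follows from the SD and the number of patients alone. It is not presented as the effect seen at 20 g/d or at any other dose, so the disputed clause feeds no number in the SAP.

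**4. What if effect shrank with dose?** Suppose 3.3 points were the effect at the cited exposure.

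| Share of 3.3 | Difference | Power, 15 per arm | Power, 12 per arm |
|---|---|---|---|
| 75% | 2.475 | 56% | 46% |
| 49.5% | 1.63 | 28.6% | 23.5% |

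The arithmetic is right, but both premises are assumed. The documents give no liver-fat effect at 20 g/d and no dose-response. These rows therefore say nothing about this trial's actual power.

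**5. The passages side by side.** The clause in the procedures section makes three claims: use in homocystinuria, tolerability, and benefit in NASH.

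- Use in homocystinuria: the risk section calls 20 g/d the upper end of the recommended range, which leaves room for lower doses.
- Tolerability: being tolerated at 20 g/d does not conflict with being tolerated at a lower dose.
- Benefit: no study in the supplied text supports it at this dose. The pilots are unnamed, and the risk section nowhere says that its two studies are those pilots or the only ones. Its summaries answer a prompt about risks, so their silence on efficacy is weak evidence.

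**6. What on-treatment betaine would add.** It would take at most 30 assays, or 30 × 0.8 = 24 at the planned retention. A clear rise in the betaine arm would support that drug was taken. It would not show what a higher or longer exposure would do, and the documents give no betaine level from the 20 g/d studies for comparison.

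**The case for a change.** The strongest argument for a change is that the benefit clause is the only human evidence of benefit the documents tie to this regimen, and that non-adherence is a practical worry. In the second cited study gastrointestinal events were 33% on betaine against 9% on placebo, and nine patients per group withdrew for reasons that included adverse effects, noncompliance and inconvenience. If those nine and the 17 completers make up the betaine arm (an assumption), 9 / 26 = 35% left. The remedy is cheap: a corrected sentence, a summary by arm, and assays on specimens that may already be in storage.

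Part of this stands. The rationale should say which pilots it means, with their dose, duration and benefit, and a report of the trial would be better for an adherence summary. But the withdrawals were seen over 12 months at a dose the Protocol puts at 20 g/d, so they transfer poorly to 3 months at half that. The supplied Protocol is also an ethics-committee summary. It mentions numbered visits without a schedule and a cost-effectiveness analysis described elsewhere, so silence on adherence does not show that none is recorded. Visit specimens are kept for batch analysis with no analyte named, which leaves on-treatment betaine open. The cheapness of the remedy also does not make it answer the question raised, as step 6 shows.

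**Conclusion.** No change to the plan. What is real is a citation ambiguity: one section credits benefit to the trial's regimen, and another places the described liver-disease studies at 20 g/d, a ratio of 2.02. The two sections must be reconciled, but that is editorial. It alters no endpoint, sample size, analysis or result, and no view is taken here on which dose is right.

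The interpretive worry has no statistical remedy within this design. A two-arm trial of one regimen estimates the effect of that regimen. A null result applies to the dose and duration tested, and writing that into the SAP would add nothing specific to this trial. The documents already limit the claims: proof of concept, findings to be confirmed, only large effects detectable. The point also bears mainly on Aim 2, since the power arguments for insulin sensitivity and endothelial function draw on the group's own earlier data and do not use the NASH studies.

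The missing adherence measure is a gap in a summary that analysts can fill from visit records or stored specimens, without affecting the planned comparison. This conclusion assumes that the unnamed pilots cannot be identified from the text supplied. If they are the 20 g/d studies, the benefit clause is wrong as worded, but the analysis is unaffected.

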## **Statistical Plan**

**Sample Size and Data Analysis:** The study will use a single site randomized, double-mask design. Our primary analysis to examine the effect of betaine supplementation will be by change from baseline to 3-month values compared to placebo in completer analysis for all endpoints of Aims 1-3. Safety will be assessed by intention to treat. Prior to data analysis, the data will be examined for outliers. Continuous measures whose distributions are not symmetric will be transformed. In secondary analysis for all outcomes we will determine if baseline betaine determines response to supplementation.

*Insulin Sensitivity*-Basis for power calculations: In an overweight prediabetes population of 14 persons similar to that proposed in this grant and using a similar clamp protocol, we demonstrated insulin sensitivity of  $5.9 \pm 2.1$  mg/kg/min, a value significantly lower than  $8.3 \pm 1.8$  in our normoglycemic control group of 27 patients ( $P=0.0005$ ). This demonstrates likelihood that the cohort proposed will be insulin resistant. We also recently assessed insulin sensitivity by clamp before and after *placebo* in a cohort of 29 persons with impaired glucose tolerance in another 3-month randomized study. Baseline values were  $4.0 \pm 1.5$  mg/kg/min and 3 months later  $4.1 \pm 1.7$ ,  $P=0.3$ . The placebo change over time was  $0.16 \pm 0.81$ , or variance  $<4\%$ . This demonstrates the high reproducibility of clamp measures. A total of 30 patients entering this two-treatment parallel-design study, provides 80% probability of detecting a treatment difference at a paired two-sided comparison with type 1 error 0.05 significance, if the standard deviation is 0.81 and the true difference between treatments is 0.85 mg/kg/min (a between-group difference of 20% change from baseline). Given the short duration of the study, we anticipate  $\geq 80\%$  retention rate, but even 24 completers would detect difference between treatment groups of 0.96 mg/kg/min (25% change from baseline between groups).

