To calculate sample size, we estimated mean and standard deviations of flow-mediated vasodilation from our previously reported findings for a placebo-treated group composed of patients with T2D. The reported change from baseline following placebo was  $-0.9 \pm 1.2\%$  (from a baseline value of  $5.8 \pm 1.1\%$  to  $4.9 \pm 0.9\%$  at six month follow up). It is anticipated that betaine will increase flow-mediated, endothelium-dependent vasodilation by 25% compared with placebo. Therefore, we expect the mean change in the betaine group to be 1.45% (from a baseline value of 5.8% to a three month value of 7.25%). Although we will analyze the data using a mixed model, to estimate required sample sizes we used the methods of Cochran and Cox for a two-sample t-test with an alpha of 0.05 for a two-tailed test of significance and 80% power..

*Secondary Outcomes.* Secondary outcomes are considered exploratory. We recognize that this study will allow for detection of only relatively large effects.

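### The primary change-from-baseline comparison does not name the endpoint's own baseline as a covariate, and the mixed model for flow-mediated dilation does not say how baseline enters; the permitted unadjusted analysis gives up precision on that endpoint.

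*SAP*

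**What the plan says.** The opening paragraph of the SAP (Sample Size and Data Analysis) sets one primary comparison: "Our primary analysis to examine the effect of betaine supplementation will be by change from baseline to 3-month values compared to placebo". The same sentence gives its scope: "in completer analysis for all endpoints of Aims 1-3". It allows transformation of asymmetric measures, but it names no test or model for this comparison and no covariate.

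The only baseline variable given a role in any analysis is the betaine concentration, as a possible modifier of response: "In secondary analysis for all outcomes we will determine if baseline betaine determines response to supplementation". That is not the baseline of the outcome itself.

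For endothelial function the sample size rests on a two-sample t-test, with the remark "Although we will analyze the data using a mixed model". The SAP does not say whether baseline FMD is a covariate or a response in that model, nor, if a response, whether the arms share a baseline mean. The SDs used for planning come "from our previously reported findings for a placebo-treated group composed of patients with T2D", followed for six months. The expected effect is given as "Therefore, we expect the mean change in the betaine group to be 1.45" percentage points.

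Under Secondary Outcomes the SAP adds: "We recognize that this study will allow for detection of only relatively large effects". The Protocol (Research Design and Methods) has "brachial artery flow mediated dilation studies performed at baseline and after 12 weeks of randomized assignment to betaine or placebo", so the FMD baseline is already scheduled.

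**The concern.** A change score uses baseline with a slope fixed at 1. That is efficient only when the true slope of follow-up on baseline is close to 1. When the slope is well below 1, subtracting baseline adds noise, and a regression that estimates the slope does better.

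The reference to a mixed model does not settle the matter. With completers only and two time points, a group-by-time model with separate baseline means gives the same treatment test as the unadjusted change score. In one simulated data set of 24 completers both gave t = 2.870. A model with a common baseline mean gives a different and usually more precise answer. The plan therefore leaves open two analyses of different precision, and the choice could be made after the data are seen.

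What is at stake is precision and pre-specification, not validity. In a 30-person study that expects to detect only large effects, precision from data already collected should not be given up without a reason.

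**Working it through.** **Inputs (SAP).** FMD: baseline SD 1.1, follow-up SD 0.9, change SD 1.2, expected change 1.45. Clamp: baseline SD 1.5, follow-up SD 1.7, change SD 0.81, target difference 0.85 with 30 patients or 0.96 with 24 completers. Alpha is 0.05 two-sided and the power target 80%. Allocation is 1:1 (Protocol), so 15 or 12 per arm.

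**The plan's own figures.** For the clamp, a two-sample t-test gives 79.2% power for 0.85 at 15 per arm (82.0% by normal approximation) and 79.2% for 0.96 at 12 per arm. The stated 80% is reproduced. The SAP states no N for FMD. If placebo is assumed flat, a difference of 1.45 with SD 1.2 has 89% power at 15 per arm and 81% at 12.

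**Formulas.** With s0, s1 and sd the baseline, follow-up and change SDs:

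- r = (s0² + s1² − sd²) / (2·s0·s1)
- slope = r·s1/s0
- adjusted variance = s1²(1 − r²), compared with sd²
- expected cost of estimating the slope: a factor 1 + 1/(N − 4), which is 1.038 at N = 30 and 1.050 at N = 24

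**FMD on the plan's SDs.**

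- r = (1.21 + 0.81 − 1.44) / (2 × 1.1 × 0.9) = 0.58/1.98 = 0.293
- slope = 0.293 × 0.9/1.1 = 0.24
- adjusted variance = 0.81 × (1 − 0.0858) = 0.741, against 1.44 for the change
- ratio = 0.514, a 49% cut; with the slope cost 0.534 (N = 30) or 0.540 (N = 24), a cut of 46-47%

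**FMD with other follow-up SDs.** The values 1.1 (no shrinkage) and 1.3 (spread grows with the mean) are assumptions. Baseline SD 1.1 and change SD 1.2 are held fixed. All rows for the adjusted analysis include the slope cost; each pair is 15 / 12 per arm.

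| Analysis | Variance cut | Detectable difference, 80% power | Power at 1.45, placebo flat |
|---|---|---|---|
| Unadjusted change | – | 1.27 / 1.44 | 89% / 81% |
| Adjusted, s1 = 0.9 (plan) | 47% / 46% | 0.93 / 1.06 | 99% / 97% |
| Adjusted, s1 = 1.1 (assumed) | 27% / 26% | 1.09 / 1.24 | 96% / 91% |
| Adjusted, s1 = 1.3 (assumed) | 10% / 9% | 1.21 / 1.37 | 92% / 84% |

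Under the same constraint, adjustment stops helping only when s1 exceeds about 1.46 (15 per arm) or 1.44 (12 per arm). If placebo is instead assumed to repeat its −0.9, the difference is 1.45 + 0.9 = 2.35 and both methods exceed 99% power. Simulation gave matching powers, with type I error of 0.049 to 0.052 for both methods.

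**Clamp.** r = (2.25 + 2.89 − 0.656) / (2 × 1.5 × 1.7) = 0.879. The slope is 0.996, and the adjusted variance is 0.656 = 0.81². There is no gain before the slope cost and a 4-5% variance penalty after it. Power goes from 79.2% to 77.6% (0.85, 15 per arm) and from 79.2% to 77.1% (0.96, 12 per arm).

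**Why not simply drop baseline.** For FMD, follow-up alone has variance 0.81/1.44 = 0.56 of the change, so most of the gain comes from not fixing the slope at 1. For the clamp, follow-up alone has 2.89/0.656 = 4.4 times the variance of the change, and the detectable difference at 15 per arm would be 1.80 instead of 0.86. Estimating the slope stays close to the better option on both endpoints.

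**Other endpoints.** For fasting glucose the SAP gives baseline SD 9.5 and change SD 10.3 but no follow-up SD. At 15 per arm, after the slope cost, the saving is 44%, 27% or 4% if the follow-up SD is assumed to be 8, 9.5 or 12. For liver fat the saving cannot be computed from the documents.

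**The case against.** The strongest reply is that this is a preference about efficiency. A change-score comparison is unbiased under randomisation and already uses baseline, and at 1.45 it meets the 80% target for FMD even with 24 completers. The largest saving also falls on the one endpoint for which the plan mentions a mixed model. If that model has a baseline covariate or a common baseline mean, nearly all of the gain is already obtained. The clamp, the first endpoint powered, gains nothing.

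All of this stands, and it keeps the point minor. It does not remove it, because the SAP does not say which mixed model is meant.

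The 46-47% is also less firm than it looks. The SDs are printed to one decimal, and rounding alone allows about 40-57% before the slope cost. They come from type 2 diabetes over six months rather than prediabetes over 12 weeks, and the size of that group is not given. The lower figures depend on holding the change SD at 1.2. If r were held at 0.293 instead, a follow-up SD of 1.3 would still give about 25% before the slope cost. The size is therefore best read as a range.

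**Conclusion.** The concern holds, as an improvement to consider rather than an error. As written, the plan permits an unadjusted change-score analysis for every Aim 1-3 endpoint, and its mixed-model remark does not rule that out for FMD.

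On the plan's own FMD SDs, that analysis carries nearly twice the variance of a baseline-adjusted one (1/0.534 = 1.9 at 15 per arm). At 24 completers its detectable difference of 1.44 leaves almost no margin against the expected 1.45 if placebo is flat. Adjustment would bring it to 1.06 on the plan's SDs, or to 1.24 or 1.37 under the assumed follow-up SDs.

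A gain computed wholly from the documents' figures is shown for FMD only. For glucose it depends on an assumed SD. For the clamp there is a small loss. Confidence in the size is moderate because the FMD SDs come from a different population and follow-up period.

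**What to change.** State the between-arm comparison for each endpoint as the 12-week value regressed on randomised arm plus that endpoint's own baseline value, both on the same scale if a transformation is used. Using the change as the response, with the same covariate, gives the identical treatment estimate and standard error, so the change-from-baseline presentation can stay. If the mixed model is kept for FMD, state that both arms share a common baseline mean. Report the adjusted between-arm difference with its 95% confidence interval. At minimum, state before unblinding how baseline enters the FMD model.

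This is a wording change with no new data. It costs one degree of freedom and, on the clamp, the 4-5% variance penalty, about two points of power.
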